7.3.2.6 Action(s) Taken

ADRs requiring action or therapy must be treated with recognized standards of medical care to protect the health and well-being of the patient. Appropriate resuscitation equipment and medicines must be available to ensure the best possible treatment of an emergency situation.

The action taken by the Investigator must be documented:

- a) in general
 - none
 - medication (other than medicinal product) or other (e.g., physical) therapy started
 - test performed
 - other (to be specified)
- b) on medicinal product
 - none
 - product withdrawn
 - dose reduced
 - dose increased

The responsible Investigator will follow-up each ADR until it is resolved or until the medical condition of the patient is stable and all relevant follow-up information will be reported to the Sponsor.

7.3.3 Serious Adverse Events

A serious AE is any untoward medical occurrence at any dose:

- results in death,
- is life-threatening (this implies that the patient was at an immediate risk of death at the time of the event, and not a hypothetical situation of what could or would have happened if, for example, no treatment had been administered),
- requires in-patient hospitalization or prolongation of existing in-patient hospitalization (hospitalization does not refer to the treatment of an ADR/AE on an out-patient status or to hospitalization because of study-related procedures (e.g., infusion at two consecutive days) or because of an elective surgical procedure for which the date had been scheduled earlier),
- results in persistent or significant disability/incapacity,
- is a congenital anomaly/birth defect,
- is another important medical event (e.g. suspected transmission of an infectious agent, or other reactions that should be reported in an expedited manner although they did not immediately result in one of the above seriousness criteria).

Medical judgment should be exercised in deciding whether an ADR/AE is serious in other situations: Important ADRs/AEs that are not immediately life-threatening or do not result in death or hospitalization but may jeopardize the patient or may require intervention to prevent one of the other outcomes listed in the definitions above, should also be considered serious.

SAE reporting timelines

All SAEs after the first administration of OctaplasTM are to be reported by telephone or e-mail immediately to the Clinical Project Manager or designee. Contact details will be communicated at the study initiation visit.

An Octapharma "Serious Adverse Event Report" must be completed and submitted within 24 hours after recognition of the event.

All SAEs should additionally be reported to:

Octapharma's Corporate Drug Safety Unit: OCTAPHARMA Pharmazeutika Produktionsges.m.b.H. [name] [contact]

E-mail: [contact]

24 hours emergency [contact] or [contact]

7.3.4 TEs and TEEs

To allow continuous monitoring of the product's safety all TEs and TEEs and other safety information as defined below must be documented and reported to Octapharma. All TEs and TEEs will be reported regardless of severity or relatedness to the product.

The following list includes diagnoses and symptoms of possible TEs and TEEs that could be expected to be reported:

Acute myocardial infarction

Increased heart enzymes*
ECG signs of myocardial infarction*
Angina pectoris*
Acute coronary syndrome*
Chest pain or pressure*
Cardiac arrest**

(Ischemic) Stroke

Transient ischemic attack

Cerebrovascular accident

Vision or speech disorders* Unilateral paresis/weakness Movement disorders* Dysphasia* Sudden severe headache*

Deep vein thrombosis

Pain or tenderness in leg(s)*
Pain in calf/calves*
Swelling calf/calves/lower legs*

Pulmonary embolism

Unexplained shortness of breath*

Sudden chest pain getting worse with a deep breath, coughing, or chest movement* Cyanosis*

Thrombophlebitis

Infusion site thrombosis

- * Possible sign or symptom of TEE
- ** May be outcome of TEE

To determine/confirm a TE or TEE the following adjudicators will be involved:

Adjudicator 1 (Investigator)

On the corresponding safety reporting form of the CRF, the Investigator is specifically asked if the reported event is a TE or TEE in his/her opinion.

Adjudicator 2 (Octapharma Central Drug Safety Unit, CDSU)

Once a TEE/TE is recorded on the CRF, the event will be forwarded to Octapharma's Drug Safety Unit who will process the TEE/TE in routine manner (including assessments of expectedness, causality, seriousness, TEE/TE classification of event).

Adjudicator 3 (Independent Data Monitoring Committee, IDMC)

The IDMC will receive anonymized case reports and/or lists of all reported adverse reactions. Serious cases, probably or possibly related and suspected TEEs/TEs (as determined by Adjudicator 1 and/or Adjudicator 2) will be reviewed on an ad-hoc basis; other cases like ADRs and not related SAEs will be reviewed on a quarterly basis. The IDMC will then vote on all new cases (simple majority), record their judgment and return their decisions back to data management.

In case, the adjudicators disagree, the following scheme will be applied (Table 1):

Table 1: Scheme of Decision for Adjudicators

Determined as	Determined as	Determined as	Determined as
TEE/TE by	TEE/TE by	TEE/TE by	TEE/TE in
Adjudicator 1?	Adjudicator 2?	Adjudicator 3?	database?
yes	no	no	yes
yes	yes	no	yes
no	yes	no	yes
no	no	yes	yes
no	yes	yes	yes
yes	no	yes	yes

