Probable: Event or laboratory test abnormality, with reasonable time relationship to drug

intake.

Unlikely to be attributed to disease or other drugs.

Response to withdrawal clinically reasonable.

Re-challenge not required.

Possible: Event or laboratory test abnormality, with reasonable time relationship to drug

intake.

Could also be explained by disease or other drugs.

Information on drug withdrawal may be lacking or unclear.

Unlikely: Event or laboratory test abnormality does not follow a reasonable time relationship

to drug intake.

Could also be explained by the patient's clinical state or by environmental factors or other therapies administered.

Not related: Reports for which sufficient information exists to conclude that the etiology is

unrelated to the IMP.

Unclassified: Reports which for one reason or another are not yet assessable, e.g., because of outstanding information (can only be a temporary assessment).

The following causality definitions should be used for classification of each ADR:

Probable: Reports or laboratory test abnormality, with reasonable time relationship to drug

intake

Unlikely to be attributed to disease or other drugs Response to withdrawal clinically reasonable

Re-challenge not required.

Possible: Reports or laboratory test abnormality, with reasonable time relationship to drug

intake

Could also be explained by disease or other drugs

Information on drug withdrawal may be lacking or unclear.

Classification of ADRs:

ADRs will be classified by the Sponsor as either expected or unexpected:

expected: an adverse event that is listed in the current edition of the Investigator's Brochure.

• unexpected: an adverse event that is not listed in the current edition of the Investigator's Brochure, or that differs because of greater severity or greater specificity.

7.3.2.5 *Outcome*

The outcome of all reported ADRs has to be documented as follows:

- 1. recovered, resolved
- 2. recovering, resolving
- 3. not recovered, not resolved
- 4. recovered, resolved with sequelae
- 5. fatal
- 6. unknown

NOTE: A patient's **death** per se is not an event, but an outcome. The event which resulted in patient's death must be fully documented and reported, even in case the death occurs within 4 weeks after treatment with medicinal product ended, and without respect of being considered treatment-related or not.

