8.6 Independent Data Monitoring Committee

An Independent Data Monitoring Committee (IDMC) will be established by the Sponsor. The IDMC will be composed of recognized experts in the field of immunology, pediatrics and/or clinical care who are not actively recruiting patients.

The IDMC will review relevant data periodically during the study and will give advice on the continuation, modification or termination of the study. A study specific Standard Operating Procedure will define in detail the composition, responsibilities and procedures of the IDMC.

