11.1. SAEs, ADRs, TEs, and TEEs

A Serious Adverse Event (SAE) is any untoward medical occurrence at any dose that

- results in death
- is life-threatening
- requires in-patient hospitalization or prolongation of existing hospitalization
- results in persistent or significant disability/incapacity
- is a congenital anomaly/birth defect
- is another important medical event

An Adverse Drug Reaction (ADR) in the context of this study is any noxious and unintended response to octaplas related to any dose; this means that a causal relationship between octaplas and the reported reaction cannot be ruled out, i.e. the relationship must be determined to be at least possibly related to administration of *octaplas* by the investigator or by Octapharma's medical expert or an adjudicator of the independent data monitoring committee (TEEs and TEs). Reactions with a missing or indeterminate causality assessment will also be classified as ADRs.

Serious Adverse Events (SAEs), Thrombotic events (TEs) and thromboembolic events (TEEs) will be handled in exactly the same fashion as ADRs in the context of the safety analysis. The only difference is that TEs and TEEs will be included in the analysis regardless of the causality assessment; even if such an event is reported as not related to study drug, it will be included in all data listings and tabulations. For the remainder of this section the term 'event' will thus be used to refer to any ADR, TE, or TEE.

All of the below will feature this classification (SAE, ADR, TE, TEE) as additional event characteristic if applicable.

All events for each patient, including multiple occurrences of the same reaction, will be listed in full detail, including reported term, MedDRA preferred term and system organ class, onset, duration, time to the event occurrence from last dose, causality, dosage, severity, seriousness and actions taken. The listing will include the number of the last infusion prior to each event and the relative time. An evaluation to identify any event with increased frequency over time will be performed.

For each age group and for the study as a whole the following will be given:

- Total number of events reported
- Number of events divided by the total number of TPEs

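### Apart from suspected TEs/TEEs, ad-hoc IDMC review is limited to serious cases rated related, so a death rated not related waits for the quarterly review

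*Protocol*

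**What the plan says.** Protocol 7.3.4 makes the IDMC the third adjudicator, after the investigator (Adjudicator 1) and the sponsor's drug safety unit (Adjudicator 2). It sets two review speeds:

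- Ad hoc: "Serious cases, probably or possibly related and suspected TEEs/TEs (as determined by Adjudicator 1 and/or Adjudicator 2) will be reviewed on an ad-hoc basis".
- Quarterly: "other cases like ADRs and not related SAEs will be reviewed on a quarterly basis".

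For thrombotic events the same section removes causality from the reporting decision: "All TEs and TEEs will be reported regardless of severity or relatedness to the product".

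Four other places bear on the rule:

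- **Protocol 7.3.3.** The first seriousness criterion is that the event "results in death". The sponsor's SAE report "must be completed and submitted within 24 hours after recognition of the event", with no causality condition.
- **Protocol 7.3.2.4.** An AE can have one of five causality ratings: Probable, Possible, Unlikely, Not related or Unclassified. The last is for "Reports which for one reason or another are not yet assessable, e.g., because of outstanding information (can only be a temporary assessment". No deadline is given for replacing it with a final rating.
- **Protocol 8.6.** The IDMC "will give advice on the continuation, modification or termination of the study". Its detailed procedures are left to a study-specific SOP that is not among the documents.
- **SAP 11.1.** For the analysis, "Reactions with a missing or indeterminate causality assessment will also be classified as ADRs".

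**The concern.** The IDMC is the only independent reader of individual cases, and it advises on whether the study goes on. For a serious event that is not a suspected TE/TEE, the speed at which the case reaches it depends on a causality rating made by an open-label investigator and by the sponsor. If both misattribute a fatal reaction to the underlying disease, the independent reading that could correct them comes only at the next quarterly review, while other children may start treatment.

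The TE/TEE route does not cover all the serious reactions the protocol expects. Section 1.3 names anaphylactic shock, citrate toxicity, severe hypotension, excessive bleeding and circulatory overload. None of these is a listed diagnosis in 7.3.4. For such events the rating can decide the timing by itself. As written, a mild suspected infusion-site thrombosis is reviewed ad hoc, whereas a fatal haemorrhage rated not related is not.

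The setting adds some weight: there is no control group (3.3.1), no interim analysis (9.4), and the appended label states that safety has not been evaluated in pediatric patients (label section 8.4).

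**Working it through.** The plan states no figure on this point, so there is none to reproduce. The check is a routing exercise followed by a small illustration of exposure.

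**Step 1: what the ad-hoc clause means.** The clause could be read as covering all serious cases. The next clause rules that out, because it names SAEs that are not related as quarterly. The condition is therefore serious and related, or suspected TE/TEE.

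**Step 2: route each causality rating of a serious case** (ratings from Protocol 7.3.2.4, rule from 7.3.4).

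| Rating | No TE/TEE suspected | TE/TEE suspected |
|---|---|---|
| Probable | ad hoc | ad hoc |
| Possible | ad hoc | ad hoc |
| Unlikely | quarterly, by default only | ad hoc |
| Not related | quarterly, stated | ad hoc |
| Unclassified | quarterly, by default only | ad hoc |

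Death appears nowhere in the rule, so a fatal case follows the same rows. One row is explicit (Not related). Two rows (Unlikely, Unclassified) follow only from the residual wording about other cases.

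**Step 3: length of the wait.** One quarter is 52 / 4 = 13 weeks, which is the maximum. If the event falls at a random point in the quarter, the mean wait is 13 / 2 = 6.5 weeks.

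**Step 4: children enrolled during the wait.** Inputs: a minimum of 40 patients (9.1) and 5 years of enrolment (3.2), that is 5 × 4 = 20 quarters. As a variant, Q1 2015 to Q4 2020 (6.2.2) is 6 × 4 = 24 quarters. Assumption: uniform Poisson accrual.

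- Expected per quarter: 40 / 20 = 2.0 (variant 40 / 24 = 1.67).
- Chance of at least one new child in a full-quarter wait: 1 − exp(−2.0) = 0.87 (variant 1 − exp(−1.67) = 0.81).
- Expected in a half-quarter wait: 1.0 (variant 0.83). Chance of at least one: 1 − exp(−1.0) = 0.63 (variant 1 − exp(−0.83) = 0.57).

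**Step 5: protocol beside SAP.** SAP 11.1 resolves missing or indeterminate causality towards the product. Protocol 7.3.4 gives such serious cases no route of their own, so they fall to the slower one. The first rule classifies events for tabulation and the second schedules committee review. They can coexist, but they lean in opposite directions on the same uncertainty.

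**The case against.** The strongest objection is that IDMC procedure belongs to the SOP announced in Protocol 8.6, which cannot be seen here. That stands for the Unlikely and Unclassified cases, where 7.3.4 is merely silent and the SOP may supply the rule. It does not stand for cases rated not related: 7.3.4 places them in the quarterly group in terms, and an SOP should not have to override an explicit protocol sentence.

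Several stronger readings are tempting, and the documents do not support them.

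- **Every fatal SAE rated unrelated waits.** No. A suspected TE/TEE goes ad hoc whatever its causality, and one call by the investigator or the safety unit is enough. The list of suspect signs is wide and includes cardiac arrest, cyanosis and unexplained breathlessness.
- **Either reader alone can delay review.** If the and/or in 7.3.4 also governs relatedness, both must withhold a related rating before the case waits.
- **The protocol treats not yet known as not related.** No text says so. Protocol 7.3.2.1 defines an ADR as a response for which a relationship cannot be excluded, and 7.3.2.4 gives ADRs only the grades Probable and Possible. A coherent reading would therefore send an unassessed serious case ad hoc. What remains is that the category is not assigned. Unclassified is also meant to be temporary, so a full-quarter wait is not its natural result, though no deadline prevents one.
- **The SAP contradicts the protocol.** It does not; one rule is for analysis and the other for monitoring.

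Other safeguards also count. All SAEs reach the sponsor quickly whatever the causality, deaths within four weeks of treatment are reported in any case (7.3.2.5, 7.3.7), and investigator or sponsor may stop the study at any time (6.2.3). None of these is independent review, but the quarterly cycle is not the only protection.

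**Conclusion.** The point holds in a limited form. A fatal or life-threatening SAE that both the investigator and the sponsor's safety unit rate as not related, with no suspected TE/TEE, waits for quarterly IDMC review by the protocol's own words. For serious cases rated Unlikely or Unclassified the protocol has a gap, which the residual wording fills with the slower route.

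The size is modest: at most about 13 weeks and about 6.5 on average, with about 2 new children in a full quarter and about 1 in an average wait. These figures assume even accrual of exactly 40 patients over 5 years; 40 is a minimum, so the rate would rise with a larger enrolment. A reader might infer about 5 children per quarter by supposing that recruitment is squeezed into 2 years (40 / 8 = 5), but nothing in the documents supports that. The time lost relative to ad-hoc review cannot be stated, because ad-hoc review has no time limit either.

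The planned descriptive analysis is unaffected. The change is worth making because it improves patient protection at little cost.

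**What to change.** In Protocol 7.3.4, redefine the ad-hoc group as:

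1. every fatal or life-threatening SAE, whatever its causality rating;
2. every SAE whose causality is probable, possible, unclassified or missing;
3. every suspected TE/TEE, as now.

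Keep the quarterly review for non-serious ADRs and for the remaining SAEs rated unlikely or not related. Repeat the same definition in the IDMC SOP so that the two documents agree. Item 2 also brings monitoring into line with the SAP's treatment of indeterminate causality, so SAP 11.1 needs no change on this point.

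The cost is one sentence in the protocol and one in the SOP. No new data collection is needed, because SAE reports are already due at the sponsor within 24 hours whatever the causality. The downside is a few extra ad-hoc case circulations to the committee in a study of about 40 children.

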7.3.5 Laboratory Tests

7.3.5.1 Determination of Blood Group

Blood samples will be drawn at Screening for determination of the patient's ABO blood group type compatibility.

7.3.5.2 Safety Laboratory Parameters

The following safety laboratory parameters will be assessed. Before each TPE and after each TPE, blood samples will be drawn for CBC and Chem 7. Within 24 hours before the first TPE procedure, during the TPE and at follow-up, ionized calcium levels will be assessed for citrate toxicity.

- Chem 7 panel:
 - o Blood Urea Nitrogen
 - o CO₂ (bicarbonate)
 - Serum Chloride
 - o Serum Creatinine
 - o Glucose
 - o Serum Potassium
 - o Serum Sodium
- CBC:
 - o White Blood Cell
 - o Red Blood Cell
 - o Hemoglobin
 - o Hematocrit
 - Mean Corpuscular Volume
 - o Mean Corpuscular Hemoglobin
 - o Mean Corpuscular Hemoglobin Concentration
 - o Red Cell Distribution Width
- Ionized calcium

7.3.5.3 Pregnancy Testing

Pregnancy testing will be done at Screening for females of childbearing potential. Confirmation that the subject is not pregnant must be established by a negative pregnancy test result obtained during Screening.

7.3.6 Vital Signs and Physical Examination

Vital signs data (heart rate, respiratory rate, temperature, and blood pressure assessment) will be collected before and after each TPE.

Physical examination data (dermatological and lymphatic system, head, eyes, ears, nose, throat, respiratory tract, cardiovascular and gastrointestinal system, musculoskeletal system, neurological system, and endocrinological disorders) will be collected at Screening.

7.3.7 Other Relevant Safety Information

Post study related safety reports: Any ADR (i.e., any adverse event with a suspected causal relationship to the medicinal product) which occurs after the completion of the study should be reported by the Investigator. The usual procedure for reporting post marketing safety information should be followed, but relation to the clinical study should be stated on the report.

If the Investigator becomes aware that a patient has died within 4 weeks after the last administration of the product, this should be reported as well, without being considered treatment related or not.

Pregnancies: Every effort will be made to avoid a pregnancy during the use of the product.

Pregnancies occurring during the study (fetal exposure to the product) need to be reported.

In case of pregnancy during the study, the Investigator is asked to complete the pregnancy notification form and to send it (by email or fax) to the Clinical Project Manager/designee.

Follow-up information on the outcome of both mother and fetus will be requested by a Sponsor representative.

Overdose, interaction, abuse, misuse, and medication error:

The following safety relevant information should be reported as an ADR or, if the reaction fulfils one of the criteria for seriousness, as a serious ADR.

Drug overdose: An overdose is a deliberate or inadvertent administration of a treatment at a dose higher than that specified in the protocol, and higher than the known therapeutic dose and of clinical relevance. The reaction must be clearly identified as an overdose. Due to the study design, no overdose is expected.

Interaction: A drug interaction is a situation in which a substance/medicinal product affects the activity of the study drug, i.e., the effects are increased or decreased, or they produce an effect that none of the products exhibits on its own. The reaction must be clearly identified as drug interaction.

Abuse: An abuse is the deliberate use of a medicinal product that may lead to addiction accompanied by harmful physical or psychological effects. This is not relevant for the medicinal product but may be applicable for concomitant medications.

Misuse: Misuse is the deliberate administration or use of the medicinal product outside its described indication or outside the current state of the art medical practice (off-label-use). The reaction must be clearly identified as misuse.

Medication error: Medication error involves the inadvertent administration or unintended use of a medicinal product which may be caused by the naming, presentation of pharmaceutical form/packaging and instructions for use/labeling. The reaction must be clearly identified as a medication error. Due to the study design, no medication error should happen.

7.4 Appropriateness of Measurements

Only standardized measurements that are widely used and generally recognized as reliable, accurate, and relevant will be used in this study.

